C. FOCUS: Effectiveness and readiness for implementation (pilot EF). We conducted a comparative effectiveness trial (RCT) 35 comparing FOCUS to a widely used an evidence-based group intervention (WRAP) in community mental health settings (n=163) (PCORI CER140311403). Results: FOCUS participants had better treatment commencement (90% vs. 58%), better continuous full engagement in treatment, equivalent (high) treatment satisfaction, and equivalent significant improvement in clinical outcomes: general psychopathology (SCL-9 Cohen's d=.44) depression (BDI-2 Cohen's d=.31), and recovery (RAS Cohen's d=.38). These moderate/large effects are clinically meaningful and comparable to more time/labor/resource intensive clinic based interventions.36 Patients rated the FOCUS intervention supported by EF as highly acceptable. Dropout in the FOCUS arm was very low (3.5%). Engagement was associated with clinical outcomes: more weeks of full engagement (defined as 5+ days of weekly use) were significantly associated with larger increases in recovery scores post-treatment. Patients who completed at least 8+ "fully engaged" weeks showed greater improvements in general psychopathology, depression, and recovery than those who did not. Relevance for implementation: CMHC providers and organizational leaders indicated a strong acceptability and interest in adoption and integration of mHealth in their programs. These findings were supported by responses to implementation survey items (rated 1-"Not at all" to 5-"Very Much"): I would be supportive of incorporating FOCUS into standard practice at my agency: M= 4.9; Connecting with clients through their smartphones would improve their quality of care: M=3.9; Connecting with clients through smartphone intervention would make me more effective in my job: M=4.25). Relevance for implementation: The FOCUS intervention required training and supervision of a single external facilitator who engaged with patients and supported and trained CMHC providers from a centralized location. The EF was not part of the CMHC clinical staff but hired and trained specifically for this role. 58 The clinical training materials and supervision structure was adapted and refined over the course of the 3-year study.

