Randomization will occur at the level of the clinic and will be balanced within study arm by number of patients served and rural/urban designation. Study sites (k=20) will vary in staffing and services capacity. Sites will either be randomized to have an internal facilitator (IF) or external facilitator (EF). The internal and external facilitators will work to engage participating organizations, practitioners, and patients throughout the study which includes sending email and placing phone calls with participating organizations, practitioners and patients in order to conduct the study (i.e., schedule appointments, request materials, etc.). They will provide updates about study progress and will maintain and request data from the study sites.

Patient Participants

After consenting into the study, patient participants will receive a phone call prior to each assessment (OM, 3M, 6M) letting them know they will receive a text or email (for those who have identified trouble receiving text messages) with the assessment URL and to provide instructions for how to complete the assessment (ensure they are in a private place, have reliable data for transmission, will take aprox. 20-30 minutes to complete, etc). Participants will then receive the web-based baseline assessment via text and will be asked to complete it in a private and quiet space. For those who have expressed difficulty completing the assessment through the web-based assessment, a phone call can be conducted with trained assessor to ask questions directly over the phone. Afterward, they will be asked to meet with their assigned facilitator (IF/EF) to install the FOCUS app on their phone, describe how to use it and set up a time for their weekly calls. This may be done via phone call, or video call, whichever is preferred by the participant. Participants will continue to use the program for 3 months in their own environments, along with participating in weekly calls to discuss what they've learned in the FOCUS app and how those strategies can help support their symptom coping strategies.

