- A list of active participants will be generated either through culling EMR data or talking with clinical teams that will serve as the primary list for their clinical teams to approach to describe the study and gauge interest.
- Services billed- no identifiers will be shared with the research team

Mental Health Provider Participants:

Select mental health providers will be invited to complete an online assessment with the research team. Staff participants will be invited to complete a confidential online survey. This includes exposure to the FOCUS app, if strategies or the program was incorporated into their treatment plans, and perceptions of how the program was adopted and implemented at their clinic.

Mental Health Provider Assessment:

Providers who receive FOCUS data

- Offered mHealth, i.e., the percent of each practitioner's eligible patients who are offered FOCUS
- Treatment Initiation, i.e., percent of consenting patients who followed their practitioner's guidance and went on to download FOCUS onto their smartphone and interact with the system at least once. Dashboard Use, i.e., the average number of times each practitioner logs on to the online FOCUS dashboard to view their individual patients' uploaded FOCUS data

The following will be captured via online confidential** survey (Qualtrics):

- The perception among practitioners that an innovation is agreeable, palatable, or satisfactory. (Measured via AIM / IAM / FIM).
- ORIC: Organizational Readiness for Implementing Change

Providers at the clinic who may not have been directly involved with the FOCUS Intervention (to provide contextual factors) through online confidential survey (Qualtrics):

- Organizational Readiness to Change Assessment (ORCA)
 - CMHC staff participants will complete 23 items using a 5-point bipolar rating scale (1-Strongly agree to 5-Strongly disagree). Constructs evaluated include clinical cooperation within the practice, clarity in patient care goals and process, level of support (e.g., training, budget, staffing) and typical receptivity to guidance (staff) and feedback (leadership).
- Absorptive capacity will be measured among CMHC practitioners who were engaged in IF or EF implementation at 0, 3, and 6 months using the 14-item ACAP Scale.
 - o The ACAP Scale evaluates dimensions of absorptive capacity including
 - Acquiring (e.g., searching for new information, motivation to use information)

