In Aim 2, mediation will be tested using the product of coefficients approach for multilevel mediation analysis, building on the models in Aim 1. In this approach, the total effect of the implementation strategy is parsed into direct and indirect pathways associated with absorptive capacity, the mediator. Path "a" will represent the effect of the implementation strategy at the organizational level on the clinician-level assessment of absorptive capacity. Path "b" represents the relationship between this mediator and the clinician-level growth parameter, signifying change in outcomes over time. An unbiased estimate of the mediated effect is derived via the product of the "a" and "b" paths (i.e., a\*b) from these analyses. We will test the statistical significance of the mediated effects using the joint significance test and use Monte Carlo simulation methods to derive confidence intervals. Separate mediation models will assess whether absorptive capacity mediates the relationship between implementation strategy and, respectively, penetration, cost, and acceptability outcomes. Moderators of the implementation strategies' effects will be tested by adding terms for each hypothesized moderator and its interaction with the implementation strategy to the Aim 1 models. Specifically, these models will estimate the conditional relationships between the implementation strategies and implementation outcomes across different values of the putative moderators. Organization-level moderators (i.e., Readiness for Change, Organizational Culture, Urban or Rural designation) will be examined. The magnitude of the moderator effects will be probed using simple slopes analysis and region of significance analysis for multilevel models.

In Aim 3, we will use the same techniques as described in Aim 1 to develop 3-level linear mixed regression models that account for the nesting of time within patient and patient within organization to assess the impact of the implementation strategy on patient outcomes over time. We will use the methods described in Aim 2 to examine whether this relationship is moderated by organizational moderators and selected patient demographic characteristics (i.e., gender, race). We will also determine if patients' level of mHealth engagement mediates the relationship between implementation strategy and patient outcomes. All analyses will be conducted using MPlus to

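### The SAP calls the a*b product for absorptive capacity unbiased, but path b is observational and unadjusted, so common causes of mediator and outcome change bias it up or down whenever the strategy moves the mediator

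*SAP*

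**What the plan says.** In the SAP's Analytic Approach, the Aim 2 paragraph builds the mediation analysis on the Aim 1 growth models.

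- Path a runs from the clinic's assigned strategy to each clinician's absorptive capacity score.
- For path b, the SAP's definition is that it "represents the relationship between this mediator and the clinician-level growth parameter, signifying change in outcomes over time".
- The SAP then says: "An unbiased estimate of the mediated effect is derived via the product" of the two paths. No condition is attached.
- On inference: "We will test the statistical significance of the mediated effects using the joint significance test". Confidence intervals come from Monte Carlo simulation.

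For Aim 3 the SAP will also examine whether patients' "level of mHealth engagement mediates the relationship between implementation strategy and patient outcomes". It does not spell out a separate estimator there and does not repeat the claim of unbiasedness.

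On what is randomised, Protocol 5.1 (Study Sites) says: "Randomization will occur at the level of the clinic". Balance is sought on urban or rural setting and on the number of patients served.

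On mediator timing, Protocol 5.1 says: "Absorptive capacity will be measured among CMHC practitioners who were engaged in IF or EF implementation at 0, 3, and 6 months". Protocol 4.1 and 8.2 place the staff surveys at month 0 and at roughly 3 months only.

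**The concern.** Randomising clinics makes the arms comparable for the strategy's effect on absorptive capacity. It does not make clinicians with high and low absorptive capacity comparable with each other. Anything that raises a clinician's absorptive capacity and also steepens that clinician's change in outcome enters path b as if it were an effect of the mediator.

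The documents themselves point to candidates. Protocol 1.8a treats organisational culture and readiness for change as drivers of implementation success, yet the SAP uses them only as moderators. Acceptability and absorptive capacity are both rated by staff on questionnaires, so response style could affect both. For engagement, Protocol 10.1 says that patients decide for themselves whether and when to use FOCUS. The pilot finding in Protocol 1.8b, that weeks of full engagement "were significantly associated with larger increases in recovery scores post-treatment", is the same kind of association with a self-selected behaviour.

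Mediation is a named objective in Aims 2 and 3, and Protocol 1.5 presents it as an evaluation of mechanisms. At stake is whether the reported indirect effect carries a property that the design does not give it.

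**Working it through.** The SAP states no figure for this property, so there is none to reproduce. The check asks what a*b estimates when path b is confounded.

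**Inputs from the SAP's Analytic Approach and Power Analysis:** 20 clinics, 5 clinicians per clinic, two-sided alpha 0.05, arm set at clinic level, and mediation declared when both paths are significant.

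**Assumed inputs, not in the documents:** path a of 0, 0.5 or 0.8 SD; an induced mediator-outcome correlation r of 0 to 0.3; a residual clinic ICC of 0.20; a linear model with the clinician's slope as outcome.

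**Closed form.** With standardised residuals, an omitted common cause that induces correlation r between mediator and outcome slope, given arm, shifts path b from b to b + r. Then

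mean a*b = a × (b + r), so the bias is a × r.

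With true b = 0 and a = 0.5: 0.5 × 0.1 = 0.05, 0.5 × 0.2 = 0.10 and 0.5 × 0.3 = 0.15. A confounder equally correlated with both variables needs a correlation of √r with each to do this: √0.1 = 0.32, √0.2 = 0.45 and √0.3 = 0.55.

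**Simulation check** (1,500 runs per cell; path a tested on clinic means with 18 df; path b by least squares with a clinic-robust standard error; true mediation zero; clinician-level confounder):

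| a | r | mean a*b | path b significant | mediation declared |
|---|---|---|---|---|
| 0 | 0.3 | 0.002 | 81.9% | 3.9% |
| 0.5 | 0 | -0.001 | 6.3% | 3.3% |
| 0.5 | 0.1 | 0.049 | 18.0% | 6.5% |
| 0.5 | 0.2 | 0.100 | 49.7% | 21.5% |
| 0.5 | 0.3 | 0.153 | 83.2% | 39.5% |
| 0.8 | 0 | 0.000 | 5.6% | 4.2% |
| 0.8 | 0.1 | 0.079 | 14.8% | 12.0% |
| 0.8 | 0.2 | 0.161 | 47.9% | 40.0% |
| 0.8 | 0.3 | 0.243 | 82.3% | 70.1% |

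The means agree with a × r. With a clinic-level confounder at a = 0.8 and r = 0.3, the mean was 0.229 and mediation was declared in 36.5% of runs.

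**Direction.** With a real mediated effect of 0.8 × 0.3 = 0.24 and confounding of strength 0.3:

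- Same direction on mediator and outcome: mean a*b 0.479, about double the truth.
- Opposite directions: mean a*b -0.006, declared in 5.8% of runs, so a real effect is hidden.

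**Effect of adjustment.** With the confounder itself added to the path b model (a = 0.8, r = 0.3, true mediation zero), the mean was -0.005 and mediation was declared in 5.2% of runs. This shows what adjustment achieves for a measured cause. It says nothing about unmeasured ones.

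**The case against.** A reader might infer that any factor driving both mediator and outcome would be reported as mediation. The documents do not support that.

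- The joint test also requires path a. With a = 0, mediation was declared in at most 3.9% of runs, however strongly path b was confounded.
- Confounding can hide mediation as well as create it.
- Path b targets growth, so a factor that shifts only the level of the outcome largely drops out.

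A reader might also infer that the SAP claims unbiasedness for engagement. It does not: the word is attached only to the absorptive capacity product. Nor does any passage say that a significant indirect effect would be taken as a proven mechanism. The Power Analysis section accepts openly that some leads may prove wrong.

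The sizes are open to challenge too. The confounding strengths are assumed. At a = 0.5 and r = 0.1 the false-declaration rate is 6.5% against 3.3% without confounding, which is modest. The 70.1% figure needs a = 0.8 and a confounder correlated about 0.55 with both variables. The formula is linear and does not carry over to penetration rates modelled by negative binomial regression.

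All of this stands, and it limits the point. It does not rescue the word. If unbiased under the model's assumptions was meant, the assumption has to be written down. The only ignorability statement in the SAP concerns drop-out, which is a different matter. The joint significance test and Monte Carlo intervals deal with sampling error and cannot detect confounding.

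**Conclusion.** The point holds in limited form. The SAP attributes to the absorptive capacity product a property that randomising clinics does not provide, and it plans nothing to protect path b. The bias is a × r in a linear standardised model. It can go either way and vanishes if the strategy does not move the mediator. With an assumed a of 0.5 and no true mediation it is about 0.05 to 0.15 for r between 0.1 and 0.3. These are illustrations over an assumed range, not forecasts for this trial, and they apply to continuous outcomes only.

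Engagement has the same identification problem because patients choose their own use, but there the gap is an unstated assumption and not a false claim. The comparison of the two strategies on the outcomes themselves is unaffected.

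**What to change.** 1. Replace the claim of unbiasedness with a statement that a*b estimates the mediated effect only if there is no unmeasured confounding of mediator and outcome. Say that this applies to engagement as well.
2. In the path a and path b models for absorptive capacity, adjust for the month-0 absorptive capacity score and the randomisation factors (urban or rural, number of patients served). Confirm that the month-0 score is taken before facilitation begins. For engagement only the randomisation factors apply, since prior FOCUS use is an exclusion criterion and no baseline value exists.
3. Do not add the baseline outcome as a further covariate. It is already a time point in the growth model.
4. For continuous outcomes, report beside each indirect effect the mediator-outcome residual correlation that would bring it to zero. Do not extend this output to the negative binomial rates.
5. Word positive results as consistent with mediation.
6. Reconcile the absorptive capacity visits (0, 3 and 6 months in Protocol 5.1; staff surveys at 0 and about 3 months in Protocol 4.1 and 8.2), and state which visit enters path b.

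The cost is SAP wording and one sensitivity output from data already planned. The downside is a few more parameters with 20 clinics. The adjustment does not remove unmeasured confounding, which is why items 1, 4 and 5 are needed alongside it.

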## UNIVERSITY of WASHINGTON

Analytic Approach. Our analyses seek to test the overall effect of our implementation strategies on implementation outcomes (Aim 1), mediators and moderators of those effects (Aim 2), and the impact of the strategies on patient outcomes (Aim 3). In Aim 1, the dependent variables of interest will be penetration and provider acceptability assessed at baseline (prior to initiation of the facilitation strategies), at 3 months (following the completion of the facilitation period), and at 6 months (following 3 months of having no exposure to facilitation). Given the nested data (i.e., time nested within clinicians and clinicians nested within agencies), analyses will rely on 3-level mixed effects regression models. Negative binomial regression with log offsets will be used to model rates, and linear regression will be used to model continuous outcomes. For all models, our independent variables of interest will be a binary indicator of internal versus external facilitation (measured at the organizational level), time, and their interaction. The magnitude and statistical significance of the interaction term will estimate the effect of the implementation strategy on change, or "growth," in outcomes over time. The impact of the intervention strategy on each outcome at each time will also be derived from these models. In addition, we will aggregate facilitylevel data and estimate the average weighted cost metrics across the sample of sites. Future commercial pricing of mHealth technology is unknown, so we will run scenarios that have different ranges of costs for FOCUS and explore the impact on the total program costs.

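### Moderation is tested on moderator × strategy, although the strategy effect in these models is strategy × time; for repeated linear outcomes the tested coefficient averages in baseline and does not measure moderation of change

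*SAP*

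**What the plan says.** All of this is in the SAP, under Analytic Approach unless noted.

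- **Aim 1, model terms.** "our independent variables of interest will be a binary indicator of internal versus external facilitation (measured at the organizational level), time, and their interaction".
- **Aim 1, which term is the effect.** "The magnitude and statistical significance of the interaction term will estimate the effect of the implementation strategy on change". A second read-out follows: "The impact of the intervention strategy on each outcome at each time will also be derived from these models".
- **Aim 1, timing.** Outcomes are "assessed at baseline (prior to initiation of the facilitation strategies), at 3 months (following the completion of the facilitation period), and at 6 months".
- **Aim 2, moderators.** Moderation is tested by "adding terms for each hypothesized moderator and its interaction with the implementation strategy to the Aim 1 models". The results are probed by simple slopes and regions of significance.
- **Aim 2, mediation.** Path b is "the relationship between this mediator and the clinician-level growth parameter, signifying change in outcomes over time", so here the plan does tie the analysis to growth.
- **Aim 3.** "We will use the methods described in Aim 2 to examine whether this relationship is moderated by organizational moderators and selected patient demographic characteristics".
- **Power Analysis.** Detectable organizational moderator effects are d=0.50 for patient outcomes and d=0.61 for provider outcomes. The coefficient they refer to and the moderator's distribution are not stated.

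The protocol (section 4.1, staff participants) gives staff assessments at 0 and about 3 months only, whereas the SAP has three waves.

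**The concern.** If the strategy effect is a difference in change, its moderation is a difference in that difference, which is the moderator × strategy × time term. The SAP's moderator rule names only two additions, the moderator and its product with strategy. Such a model forces the moderator difference in the arm gap to be the same at 0, 3 and 6 months, and it does not let strategy × time vary with the moderator. Baseline precedes facilitation, so there is no strategy effect at that wave to moderate.

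Two things are at stake. Real moderation of change is shrunk towards zero. A chance baseline difference in the arm gap between, say, high- and low-readiness clinics can be read as moderation. The simple-slopes and region-of-significance results inherit the same parameter, as do the Aim 3 analyses by organizational factor, gender and race.

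**Working it through.** **1. The plan's own base figure.** Inputs from Power Analysis: 20 clinics, 15 patients each, ICCs 0.19 (organization) and 0.45 (patient), two-sided alpha 0.05, 80% power. A 10:10 split of clinics is assumed, since no ratio is stated. One reading of the ICCs reproduces d=0.44:

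- clinic variance 0.19×0.45 = 0.0855; patient variance 0.81×0.45 = 0.3645; residual 0.55
- variance of a clinic mean over three waves = 0.0855 + 0.3645/15 + 0.55/45 = 0.1220
- detectable d = 2.80 × √(2×0.1220/10) = 0.438

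This is a time-averaged arm difference. That suggests, but does not prove, that power was computed for a level and not for strategy × time.

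**2. What the moderator × strategy coefficient estimates.** Let δ₀, δ₃, δ₆ be the true moderator difference in the arm gap at each wave, with δ₀ = 0 and full moderation scaled to 1. In a balanced linear model with random intercepts the fitted coefficient is the plain mean of the waves.

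| True pattern | Coefficient |
|---|---|
| Full at months 3 and 6 | (0+1+1)/3 = 0.67 |
| Linear growth | (0+0.5+1)/3 = 0.50 |
| Full at 3, half at 6 | (0+1+0.5)/3 = 0.50 |
| Month 3 only | (0+1+0)/3 = 0.33 |
| Two waves, 0 and 3 | (0+1)/2 = 0.50 |

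With moderator × time and the three-way term added, the first pattern returns 1.0 at months 3 and 6, and the two-way coefficient becomes the baseline difference, 0. If random slopes are assumed (variance 0.02 clinic and 0.05 patient per 3 months), the three-wave patterns return 0.22 to 0.39 in the two-way model.

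A chance gap of 0.30 that is present at baseline and persists, with no moderation of change, gives (0.30+0.30+0.30)/3 = 0.30.

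**3. Power at the SAP's d=0.50, step pattern.** Assumptions: a binary clinic-level moderator with 5 clinics in each arm-by-moderator cell, so SE = √(0.8 × v); noncentral t with 16 df; clinic effects correlated r between waves. Here v is:

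- two-way: σ²c(1+2r)/3 + σ²p/15 + σ²e/45, with true coefficient 0.667×0.50 = 0.333
- three-way, mean of months 3 and 6 minus baseline: 1.5 × [σ²c(1−r) + σ²e/15], with true coefficient 0.50

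Reading A takes clinic/patient/residual as 0.19/0.26/0.55. Reading B is the one from step 1.

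| r | Reading | SE two-way | SE three-way | Power two-way | Power three-way |
|---|---|---|---|---|---|
| 0.7 | A | 0.381 | 0.335 | 13% | 29% |
| 0.7 | B | 0.290 | 0.273 | 19% | 40% |
| 1.0 | A | 0.419 | 0.210 | 12% | 61% |
| 1.0 | B | 0.312 | 0.210 | 17% | 61% |
| 0.5 | A | 0.354 | 0.397 | 14% | 22% |

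A single-wave change contrast (factor 2 in place of 1.5) has 23% power at r=0.7 under reading A.

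**4. The stated moderator figures.** Under reading B with r=1 and a normal approximation, the detectable two-way coefficient is 2.80×√(0.8×0.1220) = 0.875. The three-way figures are 2.80×√(0.8×1.5×0.55/15) = 0.59 averaged over months 3 and 6, and 2.80×√(0.8×2×0.55/15) = 0.68 at one wave. None equals 0.50. Since the moderator's distribution and the contrast are not given, this shows only that the coefficient has to be named.

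**The case against.** **The slope reading.** The SAP does not say that these are the only terms. In a growth model, entering the moderator and its product with strategy as predictors of the slope is the three-way term, and then nothing is diluted. The authors may have meant this. The SAP does not say so, however, and in the same section it names the growth parameter when mediation depends on it. The promise to derive effects at each time does not help either, because without moderator × time terms the derived moderation is the same constant at every wave.

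**Penetration.** A reader might infer that the 0.50–0.67 fractions hold for every Aim 1 outcome. They do not. Penetration rates use negative binomial models with log offsets, and its components (protocol 5.1: patients offered FOCUS, treatment initiation, dashboard use) are probably near zero before facilitation. All-zero baselines carry almost no information about a ratio. In one simulated Poisson data set with zero baselines and a true log-ratio of 0.50, the two-way coefficient was 0.44, where the linear fractions would give 0.33 or 0.25. The missing terms are the same, but little dilution follows. Cost is not described as a repeated measure. This objection stands.

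**Power.** A reader might infer that the change turns a hopeless test into a strong one. At d=0.8 with perfectly stable clinic effects, reading A does give 22% against 95%. But the SAP's own moderator effects are 0.50 and 0.61, nothing in it says clinic effects are stable, and at r=0.5 the three-way SE is the larger of the two. This objection also stands.

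**Baseline gaps.** Clinics are randomized, balanced on size and rural/urban designation (protocol 5.1). A differential baseline gap is therefore chance variation and not systematic bias, although with 20 clinics, and no stated balancing on readiness or culture, it need not be small.

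**Standing.** Moderation is secondary, and the SAP openly prefers following leads to missing them. That lowers the severity but does not make the coefficient the right one.

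**Conclusion.** The point holds for repeated linear outcomes, that is, acceptability and the patient outcomes. Followed as written, the rule tests a time-constant difference that includes baseline. It recovers about 0.67 of true moderation (full by month 3) or 0.50 (linear growth, or two waves), and it does not estimate moderation of change. The fractions assume balanced waves and random intercepts; they fall further with random slopes.

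The power gain is real but modest under plausible assumptions: 13–19% against 29–40% at d=0.50 with r=0.7, a step pattern and an even binary clinic moderator. It is larger only if clinic effects are stable. Both tests are weak at r=0.7, so correcting the term does not by itself make the moderator aims well powered.

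The documents do not support a claim of systematic bias, of the same dilution for penetration, or of any effect on cost. The main strategy test, the randomization and the data collection are untouched. This should be fixed, but it does not threaten the trial's main comparison.

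**What to change.** In the SAP, Analytic Approach, Aim 2, replace the moderator rule with wording such as:

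> Moderation of repeated outcomes is tested by adding the moderator, moderator × strategy, moderator × time and moderator × strategy × time to the Aim 1 model (equivalently, by entering the moderator and moderator × strategy as predictors of the growth slope as well as of the intercept). The test is on the three-way term: the moderator difference in the strategy effect on change from baseline.

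Then:

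- State whether the tested contrast is month 3, month 6 or their average, and align this with the staff assessment times in protocol 4.1.
- Apply the same rule in Aim 3 to the organizational moderators, gender and race, and take simple slopes and regions of significance from the three-way model.
- In Power Analysis, restate the moderator detectable effects for that term, with the assumed moderator distribution and stability of clinic effects over time.

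The cost is two extra terms per moderator beyond the current rule with linear time and a one-parameter moderator, and four or more with separate month-3 and month-6 effects or a multi-category race variable. The restated detectable effects may be less favourable than 0.50 and 0.61. No new data are needed. If the slope reading was intended all along, the change is only a clarification.
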